The sample size for primary analyses for the TXA clinical trial is 963 eligible patients (321 per group) assuming (based on the ROC Hypertonic Saline (HS) Trial)³⁸ 4% of the 1002 target enrollment will have the treatment kit opened and not given. Based on prior experience in subjects with severe TBI (GCS \leq 8) from the same clinical sites and hospitals for the TXA trial (that participated in the HS trial), head CT scans were obtained for more than 95% of subjects. In this cohort between 59% and 88% of subjects had a Marshall score > 1 (depending on site). We anticipate slightly lower rates in the TXA trial based on the eligibility criteria including both moderate and severe TBI (GCS \leq 12). To calculate the power we will have to determine if a biomarker combined with GCS improves upon GCS alone as a predictor of ICH, we simulated the power to detect odds ratios for the association of a one standard deviation higher biomarker value in a logistic model that also includes GCS based on a control-group sample size of $.90 \times 321 = 289$. Under a variety of correlations between GCS and biomarker ranging from $\pm .1$ to $\pm .5$, ORs for the association of a 1 SD lower GCS ranging from 1.2 to 2.0, and average probabilities of ICH ranging from .6 to .8, we consistently had 80% power or more to detect an OR of 1.5 associated with a one SD higher biomarker value (in some settings we had more than 80% power to detect an odds ratio of 1.4). These are consistent with ORs associated with these biomarkers that have been found in a number of smaller studies.⁴⁵⁻⁴⁸

References Cited

4. Injury prevention and control: traumatic brain injury. Centers for Disease Control and Prevention web page. <http://www.cdc.gov/traumaticbraininjury>. Accessed May 10, 2014.
5. Carey ME. Analysis of wounds incurred by US Army Seventh Corps personnel treated in Corps hospitals during Operation Desert Storm, February 20 to March 10, 1991. *J Trauma.* 1996;40:S165-169.

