Hypothesis 3: Elevated circulating biomarkers measured within 2 hours of TBI improve outcome prediction as measured by the Disability Rating Scale (DRS) and Glasgow Outcome Scale-Extended (GOS-E) at 6 months.

The tertiary aim incorporates biomarker and clinical data obtained early after injury in patients enrolled in the control arm of a large prehospital clinical trial to determine if adding biomarkers to the well-validated IMPACT core model (including age, GCS motor score, pupillary reactivity) improves 6-month outcome prediction. This would provide a basis to inform treatment decisions and inclusion criteria for enrollment in future clinical trials.

In addition to the aims above, we propose to leverage the resources of this large clinical trial to create a genomic and transcriptomic specimen repository from sequential time points very early after injury in patients enrolled in the Prehospital TXA for TBI Trial. This unique repository from patients with moderate or severe TBI will allow future examination of systemic genomic and transcriptomic changes that occur after TBI. Future studies resulting from this repository have the potential to provide diagnostic, prognostic and therapeutic insight that would significantly advance the understanding of the pathophysiology of TBI.

C. INNOVATION

The Prehospital TXA for TBI Trial is the first large clinical trial to randomize patients to receive a potential therapeutic drug for moderate or severe TBI in the prehospital setting within 2 hours of injury. Approximately 1000 patients will be enrolled at 10 centers across the US and Canada under an FDA Exception from Informed Consent to determine if early administration of TXA is effective for improving outcome measured 6 months after injury. Because patients will be randomized by first-responders at the injury scene and followed for 6 months, this provides a unique opportunity to validate the most promising brain-specific serum biomarkers.

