Samples will be obtained from 5 time points for all patients (arrival to ED, 6, 12, 24, and 48 hours after study randomization). This limited sampling scheme will enable an estimate of PK parameters (with less confidence than in the extensive sampling group), with the exception of $t_{1/2}$ which will remain robust. Analyses will focus on the extensive sampling cohort with the exception of $t_{1/2}$ which will be extended to all subjects.

E. ANALYSIS PLAN

Analysis plan for the aims of this study:

Hypothesis 1.1: Elevated biomarkers measured within 2 hours of TBI more accurately predict ICH and brain injury pattern and severity on initial computed tomography (CT) scan than GCS.

As preliminary analyses, we will use logistic regression to examine whether initial levels of brain-specific biomarkers (GFAP, UCH-L1, SBDP150) are associated with the presence of ICH on initial CT scan in subjects in the placebo arm. In patients with evidence of brain injury (Marshall score >1), we will also examine the association with mass lesions vs diffuse injury.

To examine whether initial brain-specific biomarker levels (GFAP, UCH-L1, SBDP150) improve upon GCS in predicting presence of injury, we will create Receiver Operating Characteristic (ROC) curves that describe the sensitivity and specificity profiles of each individual biomarkers for predicting the presence of ICH on initial CT scan. We will compute the area under the ROC curve (AUC) as a summary measure of the predictive ability of each biomarker and compare it to the AUC based on the GCS alone. A confidence interval for the difference in AUCs will be computed using Delong's method.⁴¹

To examine whether combinations of the initial brain-specific biomarker levels (GFAP, UCH-L1, SBDP150) improves upon GCS or whether one or more of these biomarkers together with GCS improves upon the GCS alone in predicting presence of injury or injury pattern, we will adopt a 10-fold cross-validation approach⁴² to develop multivariable predictive models based on combinations of biomarkers and combinations of biomarkers and GCS. Levels of the three biomarkers and the GCS will be candidate variables in these models, which will relate the probability of ICH outcome, p , to biomarkers and GCS and possibly their interactions x_1, \dots, x_n , as follows: $\log(p/(1-p)) = b_0 + b_1x_1 + \dots + b_4x_n$.

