Without the need to reserve a separate validation data set, ten-fold cross-validation reduces the optimistic bias inherent in evaluating the AUC based on the same data used to fit the model since the evaluations depend on the tent of the data not used to fit the model. We will pick the best predictive model size based on the maximal cross-validated AUC estimate, and our final predictive model will be based on the model of this size that maximizes the likelihood for the full sample. Secondary analyses to obtain models with high clinical utility will use this same cross-validation approach to identify and evaluate good tree-based models using classification and regression tree (CART) methodology.⁴³ We will also fit the predictive model to all subjects in the three treatment arms, and examine interaction terms that allow for different associations in the different arms. If no significant interactions are detected, we will develop a single predictive model using data from subjects in all treatment arms combined.

Hypothesis 1.2: Biomarkers that remain elevated or subsequently increase during the first 48 hours after injury are associated with ICH progression and an increased 28-day mortality.

Additional goals under Specific Aim 1 are to examine whether there are associations between trends in serial biomarker levels during the first 48 hours after injury and two outcomes: ICH progression and 28-day mortality. To examine these relationships we will treat the biomarker level as the outcome and use linear mixed models to account for the correlation of the multiple biomarker measurements within subjects. The mixed models will allow us to test whether both types of clinical measures are associated within-subject biomarker mean levels and slopes over time.

Hypothesis 2.1: In TXA treated patients compared to placebo, decreased biomarkers measured serially during the first 48 hours after TBI are associated with a favorable long-term outcome.

Preliminary analyses will use linear mixed models, as above, to examine whether treatment group is

related to mean levels and subject-specific slopes in serial measurements of brain-specific biomarkers (GFAP, UCH-L1, SBDP150) over the first 48 hours after injury. We will also examine whether favorable outcome of GOS-E at six months is related to mean levels and slopes in biomarkers within 48 hours of injury.

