Among controls, we will relate initial brain-specific biomarker levels (GFAP, UCH-L1, SBDP150) to poor clinical outcome (GOS-E < 5) at six months by fitting logistic regression models. Using single-variable linear logistic models, preliminary descriptive analyses will compute the crude OR for poor outcome associated with a one standard deviation difference in the biomarker and a 95% confidence interval.

To develop a multivariable predictive logistic model including brain-specific biomarkers that might improve upon the IMPACT Core Model,^{9,10} we will adopt a 10-fold cross-validation approach like the one to be used under the analysis for Specific Aim 1. All variables in the IMPACT Core model together with initial values of GFAP, UCH-L1, and SBDP150 and all squares of continuous variables two-way interactions between variables will be candidate variables for this model. As for analyses under Specific Aim 1, model size will be chosen by cross-validation, and the best final predictive model of that size will be identified from all the control-group subjects. Secondary analyses to obtain models with high clinical utility will also use this cross-validation approach to identify and evaluate good tree-based models using CART methodology.

As an exploratory analysis, we will also fit our predictive model to the combined data including control-arm and treatment-arm subjects, and allow interactions between TXA treatment (placebo, bolus-only, and bolus plus infusion) and all variables in the predictive model from controls. Significant interaction terms in these models could be used to generate hypotheses about the types of patients who benefit most from treatment for examination in future trials. If no significant interactions are detected, we will develop a single predictive model to data from subjects in all treatment arms combined.

Sample size justification

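### Ancillary biomarker models (Appendix 3): size is chosen at the maximal cross-validated AUC and no other evaluation is described, so the reported AUC is likely to be modestly optimistic

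*Combined protocol and SAP*

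**What the plan says.** Appendix 3, Section E describes two model-building exercises, each developed first in the placebo arm.

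- **Hypothesis 1.1** predicts ICH on the initial CT, with GCS as comparator. "Levels of the three biomarkers and the GCS will be candidate variables in these models", with possible interactions. On size: "We will pick the best predictive model size based on the maximal cross-validated AUC estimate". The final model is the one of that size with the highest likelihood in the full sample. The justification is: "Without the need to reserve a separate validation data set, ten-fold cross-validation reduces the optimistic bias inherent in evaluating the AUC". Secondary tree-based models are to be both found and assessed by the same cross-validation.
- **Hypothesis 3** predicts poor six-month GOS-E and aims to improve on IMPACT Core: "we will adopt a 10-fold cross-validation approach like the one to be used under the analysis for Specific Aim 1". The Core variables and the three biomarkers are candidates, and "all squares of continuous variables two-way interactions between variables will be candidate variables for this model". Then: "model size will be chosen by cross-validation, and the best final predictive model of that size will be identified from all the control-group subjects".

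DeLong's method is named for the AUC difference between each single biomarker and GCS. For the selected multivariable models Section E gives no interval, outer loop, hold-out, optimism correction or external validation. It does not say whether IMPACT Core will be refitted or used with fixed coefficients.

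**The concern.** Cross-validation gives a nearly fair AUC for a procedure fixed in advance. Here one set of folds does two jobs: it picks the size, and it is the only source of an AUC for the chosen model. The largest of several noisy estimates tends to lie above the true value of the model it points to. The comparator, GCS or IMPACT Core, is not chosen by such a search and gets no similar lift, so the difference between the two leans towards the new model.

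Whether biomarkers add to IMPACT Core is the whole question of Specific Aim 3. Section B says the answer would inform treatment decisions and the entry criteria of future trials.

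**Working it through.** **1. The plan's own figures.** The control-group size in the Appendix 3 sample size paragraph is .90 × 321 = 288.9, or 289. That paragraph claims at least 80% power for an odds ratio (OR) of 1.5 per SD of biomarker, adjusted for GCS, with no alpha stated. Simulated over the plan's grid, power is .84 to .98 at one-sided .10, .73 to .95 at one-sided .05 and .60 to .91 at two-sided .05. The claim is therefore reproduced only at one-sided .10. The documents state no AUC, no expected optimism and no power for the comparison with IMPACT Core.

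**2. Size of the search, Hypothesis 3.** IMPACT Core has three variables (age, GCS motor score, pupillary reactivity), and three biomarkers are added.
- Candidate terms: 6 main effects + 5 squares (motor score treated as continuous) + 15 two-way interactions = 26.
- Poor outcomes at the 40% assumed in Section 7: .40 × 289 = 115.6, and 115.6 / 26 = 4.4 per candidate term.
- With the 15% missing six-month outcomes assumed in Section 7: .85 × 321 = 273 subjects.

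**3. Optimism, Hypothesis 3.** Definitions:
- A_max = the largest, over model sizes, of the mean ten-fold AUC, with selection repeated inside each fold.
- A_true = the AUC of the model refitted on all controls, measured in 20,000 new subjects.
- Optimism = A_max − A_true.
- Apparent gain = A_max − AUC of Core in the sample (cross-validated, Core refitted). True gain = A_true − true AUC of refitted Core.

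Inputs from the documents: n = 289 and 40% poor outcome. Assumptions: 26 terms, forward selection in place of best subset, normally distributed biomarkers, biomarker–Core correlation .3, one active biomarker with OR 1.0, 1.5 or 2.0 per SD, and Core AUC from about .65 to .82. There were 200 replicates per row.

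| Core AUC | OR | A_max | A_true | Optimism (SE) | Apparent gain | True gain |
|---|---|---|---|---|---|---|
| .81 | 1.0 | .808 | .799 | .009 (.002) | +.002 | −.006 |
| .82 | 1.5 | .823 | .813 | .010 (.002) | +.009 | −.002 |
| .82 | 2.0 | .841 | .834 | .006 (.002) | +.025 | +.018 |
| .72 | 1.0 | .716 | .696 | .019 (.003) | −.002 | −.021 |
| .74 | 1.5 | .746 | .729 | .017 (.002) | +.011 | −.006 |
| .74 | 2.0 | .777 | .764 | .014 (.002) | +.037 | +.023 |
| .65 | 1.0 | .635 | .608 | .027 (.003) | −.007 | −.036 |
| .67 | 1.5 | .684 | .658 | .026 (.003) | +.018 | −.010 |
| .68 | 2.0 | .733 | .713 | .020 (.002) | +.056 | +.033 |

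The first column is the AUC of Core with fixed, correct coefficients; small discrepancies are rounding. Against that fixed Core the pattern is the same. For example, at Core AUC .74 and OR 1.5 the apparent gain is +.007 and the true gain −.009.

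Resubstitution optimism in the same runs was .018 to .073, so cross-validation removes a good part of it.

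In replicates where the final model was truly worse than Core, a gain was still shown in 26 to 88% (null biomarkers) and 57 to 97% (OR 1.5), across both forms of Core. These shares count any positive difference.

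**4. Optimism, Hypothesis 1.1.** With 10 candidates (4 main effects + 6 interactions) and ICH probability .7, within the plan's .6 to .8, optimism was .015 to .033.

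**5. Effect of nesting.** Nested 10 × 10 cross-validation was run with 60 replicates in each of two settings.

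| Core AUC, OR | A_max | Nested AUC | A_true | True losses shown as gains, Core refitted | Core fixed |
|---|---|---|---|---|---|
| .72, 1.0 | .713 | .689 | .696 | 45% → 10% | 25% → 8% |
| .74, 1.5 | .744 | .720 | .730 | 72% → 28% | 57% → 11% |

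Each share rests on the replicates with a true loss, about 25 to 60 of them, and so is imprecise. The nested estimate falls .007 and .010 below the truth (SE .005 and .004).

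**The case against.** The plan nowhere declares the maximised AUC to be the reported figure. It uses it to choose a size and then refits. Under Hypothesis 3 it names no summary statistic and no decision rule. That is true, and the point rests on a reading. The reading is the natural one: cross-validation is presented as the way to evaluate AUC without a validation set, the tree models are to be evaluated by it, and nothing else is offered.

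The plan claims only that cross-validation reduces optimism, and the simulation agrees.

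A reader might infer that the optimism is large enough to hide a real loss against IMPACT Core, or that it pushes the answer to yes. The documents do not support that in general. They give neither a Core AUC for this population nor a biomarker strength on which it could be based. The plan cites preliminary evidence of strong biomarkers, and at OR 2.0 there is on average a true gain. With null biomarkers the mean apparent gain, over both forms of Core, is −.015 to +.002, which most readers would take as no improvement. What remains is a shift towards the new model that matters most when biomarkers are weak.

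The quoted size rule concerns GCS; it reaches IMPACT Core only because Hypothesis 3 refers back to the approach of Aim 1. Also, the true loss in the table comes from searching 26 terms. Reuse of the folds makes that loss harder to see but does not cause it.

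**Conclusion.** The point holds as a modest one. On the natural reading, the AUC of each selected model is overstated: least when Core already discriminates well (AUC near .81), most when it discriminates poorly. At the plan's own detectable effect, OR 1.5, the overstatement exceeds the average true loss and reverses its sign. At OR 2.0 the direction of the average conclusion is right and only its size is inflated.

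These sizes depend on the assumed Core AUC, biomarker strength and correlation, and on forward selection standing in for best subset. The runs used 289 subjects; the roughly 273 left after missing outcomes were not simulated. The consequence is confined to the ancillary biomarker aims. The primary comparison of TXA with placebo is unaffected.

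**What to change.** State in Section E, for Hypotheses 1.1 and 3, how the performance of the selected model will be estimated:

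- Use nested ten-fold cross-validation, with size and terms chosen only in the inner loop and AUC taken from the outer loop; or a bootstrap optimism correction that repeats the entire selection in every resample.
- Evaluate the comparator (GCS or IMPACT Core) on the same outer folds, and say whether Core is refitted or fixed.
- Report the AUC difference with a confidence interval, and name the interval method.
- Apply the same rule to the tree-based models.

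The full-sample fit at the chosen size can stay as the final model.

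The cost is computing time and a few sentences; no further data are needed, and Section E already uses the bootstrap under Hypothesis 2.2. The reported AUC will be somewhat lower, and nested cross-validation errs slightly the other way, by about .007 to .010. That is similar to the optimism it removes when Core AUC is near .81, so the gain is clearest when Core discriminates less well. It reduces false reports of improvement but does not eliminate them.

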Hypothesis 2.2: In TXA treated patients, serum TXA levels are inversely associated with circulating biomarker levels and directly associated with long-term outcome.

In TXA-treated patients, we will use linear mixed models to examine whether pharmacokinetic (pK) parameters (AUC, C_{max}, T_{max}, T_{1/2}, clearance, and V_d) are associated with mean levels and slopes of serial levels of brain-specific biomarkers (GFAP, UCH-L1, SBDP150) during the first 48 hours after injury. Interaction terms with treatment group will allow us to test whether these associations differ by dosing regimen. We will also use logistic regression to examine whether pK parameters (AUC, C_{max}, T_{max}, t_{1/2}, clearance, and V_d) in the two dose groups are associated with favorable clinical outcome at six months based on the GOS-E. We will then (with interaction terms) examine whether these associations differ by dosing regimen.

Subsequent analyses will examine the extent to which serial biomarker levels during the first 48 hours after injury explain the association between PK parameters (AUC, C_{max}, T_{max}, t_{1/2}, clearance, and V_d) and 6-month GOS-E among those treated with TXA, and to what extent they explain the association between treatment group (placebo, bolus-only, and bolus plus infusion) and 6-month GOS-E. Taking the treatment group comparison as the example, we will fit logistic regression models relating dummy variables for the two treatment groups to the outcome of 6-month GOS-E < 5 both with and without adjustment for serial biomarker levels. We will then compare adjusted and unadjusted results from these models to estimate whether an important proportion of the treatment differences are explained by the biomarker levels. One minus the ratios of these two coefficients will

be used to estimate the proportion of the estimated association that is explained by the biomarkers. Confidence intervals for these explained proportions will be obtained using the bootstrap.⁴⁴ Similar analyses will examine to what extent the biomarkers explain the pK parameter- 6-month GOSE associations, after adjustment for and possible interaction with dosing regimen.

Hypothesis 3: Elevated circulating biomarkers measured within 2 hours of TBI improve outcome prediction as measured by the DRS and GOS-E at 6 months.

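### Hypothesis 3 of the ancillary biomarker study asks what biomarkers add to IMPACT Core, but the planned free search cannot attribute a gain to them

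*Combined protocol and SAP*

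**What the plan says.** Appendix 3, section B, sets Aim 3 as a question of increment over a named base. Data from the control arm are to be used "to determine if adding biomarkers to the well-validated IMPACT core model" (age, GCS motor score and pupillary reactivity) improves prediction at 6 months. Section E restates Hypothesis 3 as early biomarker elevations that "improve outcome prediction as measured by the DRS and GOS-E at 6 months".

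The analysis under that heading has two parts. The first is descriptive: a crude odds ratio for each biomarker against GOS-E < 5, from single-variable models. The second develops one multivariable logistic model with "brain-specific biomarkers that might improve upon the IMPACT Core Model". Its candidate pool is "All variables in the IMPACT Core model together with initial values of GFAP, UCH-L1, and SBDP150 and all squares of continuous variables", followed by "two-way interactions between variables will be candidate variables for this model". For selection, "model size will be chosen by cross-validation, and the best final predictive model of that size will be identified from all the control-group subjects". The text refers back to the Aim 1 method, where the rule is: "We will pick the best predictive model size based on the maximal cross-validated AUC estimate".

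Three things are absent. Core variables are not stated to be kept in. No Core-only model receives the same squares, interactions and search. No comparison of Core with Core plus biomarkers is defined. GOS-E < 5 is the only outcome analysed.

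**The concern.** The question concerns an increment, but the analysis produces a single selected model. If that model is set against plain Core, the two differ in two ways at once: one has access to biomarkers, and the same one has access to curvature and interactions among the Core variables. Any gain mixes the two sources. An unbiased AUC for the selected model would not separate them, so the problem is distinct from cross-validation optimism and nested cross-validation alone would not cure it. The only biomarker-specific estimates under Hypothesis 3 are crude and not adjusted for Core.

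Elsewhere Appendix 3 uses the form that is missing here. The background cites work that added two biomarkers to Core. The power statement for intracranial hemorrhage on CT concerns a biomarker in a model that already contains GCS.

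At stake is a claim of added prognostic value, which section B says would bear on treatment decisions and on eligibility for future trials.

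**Working it through.** **1. The plan's own sample size.** The Appendix 3 sample size justification gives 0.90 × 321 = 288.9, rounded to 289 controls. This reproduces. It was stated for predicting hemorrhage under Hypothesis 1.1; none is given for Hypothesis 3. Protocol section 7 assumes 15% missing 6-month outcomes, and 289 × 0.85 = 245.7, so 246 is used as a lower case. Both are assumptions for Hypothesis 3.

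**2. Candidate terms.** There are three Core variables and three biomarkers.
- Motor score continuous: 6 main effects + 5 squares + C(6,2) = 15 interactions = 26.
- Motor score categorical: 6 + 4 + 15 = 25.

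Of the 26, 3 + 2 + 3 = 8 contain no biomarker. Removing the three plain Core terms leaves 5: age squared, motor squared, age × motor, age × pupils and motor × pupils. (Of the 25, 4 remain.) These terms can improve on plain Core with no biomarker involved.

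**3. Events per candidate.** Section 7 assumes 40% poor outcome on placebo. 0.40 × 289 = 115.6 events, and 115.6 / 26 = 4.4 per candidate. With missing outcomes, 0.40 × 245.65 = 98.3, and 98.3 / 26 = 3.8.

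**4. Simulation with uninformative biomarkers.** Forward selection over the 26 terms, as a stand-in for best subset, with size chosen by the largest 10-fold cross-validated AUC. Assumed log odds ratios: 0.6 for age, -0.6 for motor score, 1.0 for pupils. The curved case adds 0.4 for age squared. The curved-plus-interaction case adds 0.3 for age squared and 0.4 for age × motor. There were 300 runs for the linear and curved cases at n = 289, and 250 otherwise.

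| Core truth, n | Mean CV AUC, search v Core | Search beats Core | Core + 3 biomarkers beats Core | Search beats same search without biomarkers | Independent-sample AUC, search v Core |
|---|---|---|---|---|---|
| Linear, 289 | 0.727 v 0.727 | 35% | 18% | 20% | 0.698 v 0.714 |
| Curved, 289 | 0.738 v 0.713 | 82% | 21% | 22% | 0.719 v 0.711 |
| Curved + interaction, 289 | 0.740 v 0.712 | 89% | 16% | 17% | 0.713 v 0.701 |
| Linear, 246 | 0.723 v 0.725 | 39% | 24% | 20% | 0.694 v 0.713 |
| Curved, 246 | 0.729 v 0.708 | 78% | 20% | 18% | 0.704 v 0.703 |

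Monte Carlo error is modest: for 35% of 300 runs, 1.96 × √(0.35 × 0.65 / 300) = 5.4 points. The final model contained a biomarker term in 35-36% of runs in the linear cases and 41-44% in the others, although no biomarker carried information.

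In the curved cases at n = 289 the gain is partly real on independent data, but it comes from Core terms. In the linear cases the selected model predicts worse than Core on independent data, so its wins on cross-validated AUC reflect selection. Once both sides have the same flexibility, the proportion of wins falls to 16-24%.

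**5. The nested alternative.** At n = 289 with 40% poor outcome and 2,000 runs per setting, a 3-df likelihood-ratio test of the three biomarkers given Core rejected in 4.5-5.8% of runs under the null, with Core linear or curved. Power for an odds ratio of 1.5 on one marker was 55-74% as the biomarker-motor correlation varied from 0 to 0.5.

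**6. DRS.** The hypothesis names DRS and GOS-E; the analysis text under it covers GOS-E < 5 only. No arithmetic is needed.

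**The case against.** The strongest reply is that Hypothesis 3 describes model development, not a test. It states no contrast, decision rule or p-value against Core, and does not say whether Core would be refitted or used as published. This stands. The comparison examined here is inferred from the plan's wording about improving on Core and from the Aim 1 method, so the accurate criticism is that the increment is left undefined.

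The plan also seeks a model that includes biomarkers, so a winning model without one could hardly be reported as a biomarker gain. This stands too. The 35-89% is not a false-positive rate for biomarkers: it counts every win of the search, and most final models held no biomarker term. It shows how far the score can move for other reasons.

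Third, Core plus three null biomarkers beats Core in 16-24% of runs. Part of any excess comes from reading the sign of an AUC difference without an interval, and a remedy resting on that difference alone would share the weakness.

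Fourth, the size depends on curvature, for which the documents give no evidence; with a linear Core at n = 289 the mean cross-validated AUCs are equal. The range is therefore conditional. The confounding of two sources of gain does not depend on it.

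Finally, dropping a Core variable is not an error in a prediction model as such. It matters here only because the aim is worded as adding to Core.

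**Conclusion.** The concern holds as a mismatch between Aim 3 and its analysis. Followed as written, the plan cannot attribute an apparent gain over plain Core to the biomarkers. With uninformative biomarkers the search beats Core in about 35-39% of runs if Core is linear and 78-89% if it is not. These figures rest on assumed effect sizes, 246 to 289 controls, 26 candidates (the motor score taken as continuous, and the imperfectly worded candidate sentence read as all two-way interactions), and forward selection in place of best subset.

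A reader might infer more, without support:
- That the plan contains a specified test that is invalid. It names none.
- That the search would miss a real biomarker effect. It was not simulated under a true effect, so nothing is shown.
- That the trial's main conclusions are affected. This is the tertiary aim of an ancillary study and does not touch the parent trial's primary, safety or monitoring analyses.

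The DRS omission is separate and follows from the text alone. A change is worth making before the ancillary data are analysed.

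**What to change.** Make this the primary Hypothesis 3 analysis: fit Core (age, motor score, pupils) and Core plus GFAP, UCH-L1 and SBDP150 on the same patients, with the Core variables retained and given the same functional forms in both models. Report the 3-df likelihood-ratio test and the cross-validated AUC difference on the same folds with a confidence interval. State how the motor score and pupils are coded.

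If the flexible search is kept, run it identically with and without biomarker terms on the same folds, nest size selection inside the cross-validation, and compare those two results rather than the search with plain Core.

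Run the same nested comparison for DRS, or remove DRS from Hypothesis 3 in sections B and E.

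The cost is wording in the ancillary analysis plan and a little more analysis; no new data are needed. The downside is limited power, about 55-74% for an odds ratio of 1.5 on one marker at n = 289 and less with 15% missing outcomes. The plan should say so, since it states no power for this hypothesis.
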